1. INTRODUCTION

1.1. Background on Cutaneous Squamous Cell Carcinoma

Cutaneous squamous cell carcinoma (CSCC) is a malignant proliferation of epidermal keratinocytes with invasion of the dermis, and is distinguished from non-invasive precursor lesions such as actinic keratoses (Nehal, 2018). The precise incidence of CSCC is not known because it is not included in most cancer registries; however, CSCC is thought to be the second most common non-melanoma skin cancer, with an increasing incidence in recent decades (Lomas, 2012)(Que, 2018)(Rogers, 2010). Worldwide incidence varies widely, with the highest incidence in Australia and the lowest incidence in parts of Africa (Lomas, 2012). The main risk factors for CSCC are advanced age, light skin, male gender, and a history of chronic sun exposure (Stratigos, 2015). Most CSCCs arise in the skin of the head and neck (HN), and this is thought to be related to high sun exposure of skin in these regions. Owing to chronic ultraviolet (UV) light-induced mutagenesis, CSCC tumors are hypermutated, with a median tumor mutation burden (TMB) of approximately 45 mutations/Mb (Chalmers, 2017).

Surgical resection is the centerpiece of clinical management of CSCC, achieving cure in >95% of patients (Kauvar, 2015). However, some CSCC patients are at an increased risk of disease recurrence, risk of disfigurement, or loss of function associated with surgical resection of locally advanced lesions. This phase 2 study will explore cemiplimab (350 mg intravenous [IV] every 3 weeks [Q3W] for up to 4 doses) in the neoadjuvant (preoperative) setting in patients with stage II to stage IV (M0) CSCC (stage II patients must have tumors that are ≥ 3 cm in longest diameter). The primary endpoint is pathologic complete response (pCR) rate. There is also an option for adjuvant (post-operative) treatment with cemiplimab.

1.2. Background on Cemiplimab

LIBTAYO[®] (cemiplimab) is approved in the United States, Canada, and Brazil for the treatment of patients with metastatic cutaneous squamous cell carcinoma or patients with locally advanced cutaneous squamous cell carcinoma who are not candidates for curative surgery or curative radiation. In the United States, it is approved with a suffix as cemiplimab-rwlc.

Cemiplimab is a high-affinity, recombinant human immunoglobulin G (IgG4^P) monoclonal antibody that binds to programmed cell death 1 (PD-1) and blocks its interaction with programmed death ligand 1 (PD-L1) and programmed death-ligand 2 (PD-L2), countering PD-1-mediated inhibition of the anti-tumor immune response. Cemiplimab is being evaluated in more than twenty phase 1 through phase 3 clinical studies in a variety of tumor types. The safety profile of cemiplimab demonstrated in these clinical trials is consistent with the expected safety profile of an anti-PD-1 antibody.

Further details on the clinical efficacy of cemiplimab for the treatment of patients with metastatic or locally advanced CSCC are provided in Section 1.3. Additional information, including preclinical and clinical safety data, is available in the Investigator's Brochure.

1.3. Efficacy of Cemiplimab in Advanced CSCC

The efficacy of cemiplimab in patients with metastatic or locally advanced CSCC who were not candidates for curative surgery or curative radiation was evaluated in 2 open-label, multi-center, non-randomized, multicohort studies: a phase 1 study (NCT02383212) that included expansion cohorts for patients with advanced CSCC, and a pivotal phase 2 study (NCT02760498). Across the 2 studies, the objective response rate (ORR) was 46.7% (95% confidence interval [CI], 35.1% to 58.6%) for metastatic CSCC (N = 75), 48.5% (95% CI, 30.8 to 66.5%) for locally advanced CSCC (N = 33), and 47.2% (95% CI, 37.5% to 57.1%) for combined CSCC (N = 108), with a median duration of follow-up of 8.1 months, 10.2 months, and 8.9 months, respectively. The duration of response exceeded 6 months in 60% (metastatic CSCC), 63% (locally advanced CSCC), and 61% (combined CSCC) of patients (LIBTAYO® USPI).

In a pilot phase 2 study of neoadjuvant cemiplimab in patients with stage III to IV HN CSCC (NCT03565783), preliminary results indicate a clinically meaningful rate of pCR (see Section 3.2.2).

2. STUDY OBJECTIVES

2.1. Primary Objective

The primary objective of the study is to evaluate the efficacy of neoadjuvant cemiplimab as measured by pCR rate per independent central pathology review.

2.2. Secondary Objectives

The secondary objectives of the study are:

- To evaluate the efficacy of neoadjuvant cemiplimab on measures of disease response, including:
 - Major pathologic response (mPR) rate per independent central pathology review
 - pCR rate and mPR rate per local pathology review
 - ORR prior to surgery, according to local assessment using RECIST 1.1
- To evaluate the efficacy of neoadjuvant cemiplimab on event free survival (EFS), disease free survival (DFS), and overall survival (OS)
- To evaluate the safety profile of neoadjuvant cemiplimab
- To assess change in surgical plan (ablative and reconstructive procedures) from the screening period to definitive surgery, both according to investigator review and independent surgical expert review
- To assess change in post-surgical management plan (radiation, chemoradiation, or observation) from the screening period to post-surgery pathology review, both according to investigator review and independent surgical expert review

2.3. Exploratory Objectives

The exploratory objectives of the study are:

- To explore baseline tumor markers for associations with treatment responses, peripheral and tumor measures associated with cemiplimab mechanism of action, and discovery of other potential predictive markers of efficacy or safety
- To describe patterns of failure (locoregional versus distant) in patients who experience disease recurrence following surgery
- To evaluate the cost implication due to changes in surgical plan during screening period versus actual surgical procedure performed
- To evaluate the cost implication due to changes in post-surgical management plan during screening period versus actual post-surgical management
- To assess the immunogenicity of cemiplimab
- To assess health-related quality of life in patients with CSCC who receive neoadjuvant cemiplimab

3. HYPOTHESIS AND RATIONALE

3.1. Hypothesis

Cemiplimab administered prior to surgery will result in a clinically meaningful pCR rate in patients with stage II to IV (M0) CSCC. The cutoff for clinically meaningful response is defined as 25%, which would provide confirmation of the efficacy signal detected in the pilot investigator-initiated study conducted at MD Anderson Cancer Center (NCT03565783).

The statistical hypothesis is provided in Section [11.1](#).

3.2. Rationale

3.2.1. Rationale for Dose Selection

The cemiplimab 350 mg IV Q3W dosing regimen was selected across the entire cemiplimab clinical development program. It is now the approved regimen, both within the United States and in selected countries globally, to treat patients with metastatic or locally advanced CSCC who are not candidates for curative surgery or curative radiation. This regimen is therefore expected to be effective in both the neoadjuvant and adjuvant settings.

3.2.2. Rationale for Neoadjuvant Cemiplimab in Locally Advanced Patients with CSCC Who Are Candidates for Surgery

This study proposes to evaluate the administration of cemiplimab earlier in the natural history of CSCC, in the neoadjuvant setting prior to surgery. The clinical benefit of immune checkpoint blockade may be greater in this setting. Emerging data in patients with CSCC treated with cemiplimab and in patients with other cancers treated with other anti-PD-1 agents in the neoadjuvant setting provide 2 fundamental observations: 1) neoadjuvant therapy is feasible and

does not result in a loss of opportunity for curative-intent surgery, and 2) preliminary clinical efficacy findings are encouraging. Efficacy endpoints in the neoadjuvant setting typically include pCR, defined as the absence of viable cancer cells in the surgical pathology sample, and mPR, defined as $\leq 10\%$ viable cells in the surgical pathology sample in patients who have not achieved pCR.

In a pilot study of neoadjuvant nivolumab for patients with resectable non-small cell lung cancer (NSCLC) (NCT02259621), 22 patients were enrolled to receive 4 weeks of neoadjuvant therapy (3 mg/kg nivolumab every 2 weeks [Q2W] X 2 doses) (Forde, 2018). Among 22 enrolled patients, 20 received the 2 planned nivolumab doses and underwent surgery, 1 patient with grade 3 pneumonia underwent surgery after 1 dose of nivolumab, and 1 patient was deemed ineligible per protocol. Among the 20 patients, the median time between the second dose of nivolumab and surgery was 18 days (range, 11 to 29 days). There were no treatment-related surgical delays as defined in the protocol. The mPR rate was 45% (9/20) and 2 pCRs were observed. Efficacy was directly associated with TMB among 11 patients who provided samples for sequencing and were evaluable for pathologic response: the mean number of sequence alterations was higher in 3 patients with mPR (311 \pm 55 mutations/Mb) than in 8 patients without mPR (74 \pm 60 mutations/Mb) (Forde, 2018).

The Checkmate 358 study (sponsored by Bristol-Myers Squibb) evaluated neoadjuvant nivolumab (240 mg Q2W X 2 doses) among 29 patients with resectable Merkel Cell Carcinoma (MCC) (Topalian, 2018). Two patients either had adverse events (AEs) or withdrew consent prior to surgery. Among the 27 patients who underwent surgery, the median time between the first dose of nivolumab and surgery was 4.3 weeks (range, 2.9 to 6.3 weeks). Pathologic response was reported according to independent central review among 17 patients (47% pCR, 18% mPR) and local pathology review among 26 patients (27% pCR). In some patients, this response avoided the need for more extensive surgery.

Because CSCC is a paradigmatic example of an immune-responsive tumor in which surgery is the mainstay of treatment (Migden, 2018), it is an appropriate setting to further study neoadjuvant PD-1 blockade. While mechanistic data are controversial and limited to preclinical studies in other tumor types, there is evidence to suggest that in the neoadjuvant setting, solid tumors may be enriched for both lymphocytes expressing immune checkpoint targets, as well as tumor antigens available for cross-priming (Melerio, 2016).

In an ongoing, investigator-initiated phase 2 pilot study at MD Anderson Cancer Center (NCT03565783), 20 patients with stage III to IV (M0) CSCC received 2 doses of neoadjuvant cemiplimab (350 mg Q3W). Clinical results indicate pCR rates were achieved in a clinically meaningful proportion of patients. All 20 patients were able to undergo surgical resection, and no patient developed unresectable or metastatic disease during the neoadjuvant treatment period.

To extend these encouraging preliminary results, this protocol describes a multicenter study of neoadjuvant cemiplimab for patients with stage II to stage IV (M0) CSCC in which the primary endpoint is pCR per independent central review. Patients with stage III or IV (M0) CSCC of head/neck, extremity, or trunk are eligible, as well as selected patients with stage II CSCC (≥ 3 cm longest diameter lesion in an aesthetically-sensitive region).

In this study, patients will receive up to 4 doses of cemiplimab in the neoadjuvant setting. The decision to increase the maximum number of doses of cemiplimab prior to surgery is based on 3 considerations: 1) Among 20 patients in the pilot study (NCT03565783), none lost the opportunity for curative surgery due to delays from receiving 2 doses of neoadjuvant cemiplimab; 2) Some patients in the pilot study achieved mPR, but not pCR, suggesting that an increase in the number of received doses may provide additional necessary time to achieve the full immunological efficacy of neoadjuvant cemiplimab; 3) In the current protocol, radiologic assessment after 2 doses will be implemented to confirm no disease progression prior to receiving the remaining doses.

3.2.3. Rationale for Adjuvant Cemiplimab Following Surgery

Adjuvant cemiplimab treatment is an appropriate option in the context of a clinical trial. Multidisciplinary expert guidelines from the National Comprehensive Cancer Network (NCCN) and European Association of Dermato Oncology (EADO)/ European Organization for Research and Treatment of Cancer (EORTC)/ European Dermatology Forum (EDF) recommend adjuvant radiation therapy in patients with positive tissue margins after surgery and in patients with extensive perineural invasion (Bichakjian, 2018)(Stratigos, 2015). The European guidelines also recommend consideration of adjuvant radiation therapy in patients who have undergone lymph node dissection, if multiple lymph nodes are involved or if extracapsular involvement is observed (Stratigos, 2015). Data supporting adjuvant radiation therapy recommendations for selected patients with CSCC are derived from retrospective studies, many of which contained heterogeneous populations (Bichakjian, 2018). Therefore, individualized decision making may integrate a variety of patient-specific factors regarding the appropriateness of adjuvant radiation therapy after CSCC resection.

Expert guidelines also describe the safety profile of radiation therapy for patients with CSCC (Bichakjian, 2018)(Stratigos, 2015). The frequency of these events depends on numerous variables, including the type, dose, and schedule of radiation therapy, and the anatomic site of the lesion. Common side effects of radiation therapy include fibrosis and change in the pigmentation of radiated skin. Uncommon but serious toxicities of radiation therapy include non-healing ulcers and necrosis of radiated tissue.

In melanoma, prospective phase 3 studies demonstrate that adjuvant administration of other anti-PD-1 antibodies for approximately 1 year decreases the risk of disease recurrence after surgical resection of stage III or IV disease (Eggermont, 2018)(Weber, 2017). In CSCC, a phase 3 study sponsored by Regeneron is ongoing to determine if approximately 1 year of adjuvant cemiplimab treatment, compared to placebo, decreases the rate of recurrence among high-risk patients who have completed surgery and adjuvant radiation therapy (NCT03969004).

In view of the high efficacy of cemiplimab against advanced CSCC and the positive phase 3 results among other anti-PD-1 antibodies in the adjuvant setting for melanoma patients, it is appropriate to evaluate cemiplimab in the post-operative setting. Therefore, Part 2 of this protocol allows adjuvant cemiplimab in patients who have not experienced disease progression or unacceptable toxicity during Part 1 (the neoadjuvant portion) of the study. An investigator, according to his or her clinical judgment, may opt to administer adjuvant radiation therapy in this study instead of adjuvant cemiplimab in Part 2. Such patients will not receive cemiplimab after this therapy but should be followed for disease recurrence and survival during the study. The data from Part 2 could inform the development of a future randomized trial to define adjuvant therapy for patients

with CSCC. However, the primary objective of this study is to assess neoadjuvant cemiplimab, not adjuvant therapy.

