9.1.5. Visit Schedule for Patients Who Discontinue Study Drug

9.1.5.1. Visit Schedule for Patients Who Discontinue Neoadjuvant Cemiplimab

Patients who permanently discontinue from neoadjuvant study drug due to disease progression (per RECIST 1.1; [Appendix 4](#)) or toxicity will undergo surgery (if clinically appropriate) and will return for post-surgical follow-up visit (EOT1). These patients must be followed for 90 days after last dose of cemiplimab for AE identification and reporting and are ineligible to receive adjuvant cemiplimab.

Patients who discontinue neoadjuvant therapy but achieve complete resection of all macroscopic disease (R0 or R1 resection) and who do not withdraw consent from the study will subsequently be followed by imaging per the schedule in [Table 3](#) (imaging at week 15 of Part 2 (± 10 days), week 30 (± 10 days), and week 48/EOT2 followed by imaging per the schedule in [Table 4](#) (every 4 months for the first 2 years and every 6 months for the third year), or until disease recurrence, whichever occurs first. Patients who undergo R2 surgical resection (residual gross disease) will be followed for survival only.

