11.3. Subgroup Analyses

Subgroup analyses will be performed to determine the consistency of treatment effect across various demographics and baseline characteristics. Between-group treatment effect, along with its nominal 95% CI, for the primary endpoint will be estimated within each category for the following subgroups:

- Age (<65 years, ≥65 years)
- Gender (Male, Female)
- Race (White, Non-white)
- Anatomic region of resected tumor (HN, Non-HN)
- Tumor stage (II, III/IV)
- ECOG status (0, 1)

As regards the DFS endpoint, a descriptive comparison will be performed between subgroups of patients who receive adjuvant cemiplimab versus adjuvant radiation therapy versus observation after surgery.

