4.4.2. Secondary Efficacy Variables

The secondary efficacy variables include:

- Major pathologic response (mPR) rate per independent central pathology review: mPR is defined as failure to achieve pCR but $\leq 10\%$ viable cancer cells in the surgical pathology sample.
- pCR rate and mPR rate assessed by local pathology review: pCR and mPR will be assessed by local pathology review.
- Objective response rate (ORR) prior to surgery by investigator assessment: ORR is determined by the proportion of patients with CR or PR based on investigator-assessed evaluation using RECIST 1.1 (Eisenhauer, 2009), where there is no requirement for confirmation of CR or PR. The objective response will be measured from the first dose of neoadjuvant cemiplimab to surgery or any other new anti-cancer therapy.
- Event free survival (EFS) is defined as time from first dose of neoadjuvant cemiplimab to the first of any of the following events: progression of disease that precludes surgery, inability to undergo complete resection (R0 or R1), disease recurrence (local, regional, or distant) for patients who undergo complete resection (R0 or R1), or death due to any cause.
 - Patients who do not have an EFS event without initiation of a new anti-cancer therapy will be censored at the last evaluable tumor assessment.
 - Patients who do not have an EFS event but initiate a new anti-cancer therapy, will be censored at the last evaluable tumor assessment prior to or on the date of new anti-cancer therapy.
 - Patients who do not have any evaluable post-baseline tumor assessment and do not die will be censored on the date of first study treatment.
- Disease free survival (DFS) is defined for patients who are free of disease (R0 or R1 resection) at completion of surgery as time from date of surgery until first recurrence (local, regional, or distant) or death due to any cause.
 - Patients who do not have recurrence of tumor and alive without initiation of a new anti-cancer therapy will be censored at the last evaluable tumor assessment.

- Patients who do not have recurrence of tumor and alive, but initiate a new anti-cancer therapy, will be censored at the last evaluable tumor assessment prior to or on the date of new anti-cancer therapy.
- Patients who do not have any tumor assessment after surgery and do not die will be censored on the date of surgery.

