5.6.2. Analysis of Secondary Efficacy Variables

The pCR rate per local pathology review, mPR rate per independent central pathology review, mPR rate per local pathology review, and ORR prior to surgery per investigator assessment will be summarized and corresponding two-sided 95% exact CIs will be calculated by Clopper-Pearson method (Clopper, 1934).

Percent residual viable tumor (%RVT) will be summarized descriptively.

Combined efficacy based on both ORR per RECIST 1.1 and pCR and mPR per pathology review may be explored.

The distribution of EFS, DFS, and OS will be estimated using the Kaplan-Meier method. The median EFS, median DFS, and median OS along with 95% CIs will be presented and Kaplan-Meier estimates with 2-sided 95% CIs at specific time points will be summarized. The Kaplan Meier curves will be presented.

As regards the DFS endpoint, a descriptive summary will be performed for each subgroup of patients who receive adjuvant cemiplimab, adjuvant radiation therapy, and observation after surgery.

Change in planned surgery will be summarized descriptively. The proportion of patients for whom the surgical management plan (at time of screening) differed from the actual surgery after neoadjuvant therapy will be summarized both by investigator assessment and independent surgical expert committee.

Change in planned post-surgical management will be summarized descriptively. The proportion of patients for whom radiation therapy (or chemoradiation) was planned during screening but not actually administered after neoadjuvant cemiplimab and surgery will be summarized.

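### The DFS summary by adjuvant option takes in patients barred from adjuvant cemiplimab, who can fall only in the radiation or observation group

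*Protocol*

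**What the plan says.** **The bar.** Protocol Section 3.2.3 says that "Part 2 of this protocol allows adjuvant cemiplimab in patients who have not experienced disease progression or unacceptable toxicity during Part 1". Section 9.1.5.1 makes this operative: patients who permanently stop neoadjuvant drug for progression or toxicity "are ineligible to receive adjuvant cemiplimab".

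**Who counts for DFS.** Under SAP Section 4.4.2, "Disease free survival (DFS) is defined for patients who are free of disease (R0 or R1 resection) at completion of surgery". Protocol Section 5.2.1 uses the same population. Section 9.1.5.1 keeps patients who discontinued early but had an R0 or R1 resection on the imaging schedules of Part 2 and follow-up.

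**The display.** Protocol Section 11.3 says that for DFS "a descriptive comparison will be performed between subgroups of patients who receive adjuvant cemiplimab versus adjuvant radiation therapy versus observation after surgery". SAP Section 5.6.2 words it as "a descriptive summary will be performed for each subgroup of patients who receive adjuvant cemiplimab, adjuvant radiation therapy, and observation after surgery". On method, the SAP says "The distribution of EFS, DFS, and OS will be estimated using the Kaplan-Meier method". Neither document restricts the patients shown by option, tabulates characteristics by option, or adds a caution about reading the groups against each other.

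**How radiation is chosen.** Protocol Section 3.2.3 reports that guidelines "recommend adjuvant radiation therapy in patients with positive tissue margins after surgery and in patients with extensive perineural invasion". Sections 3.2.3 and 6.1.3 leave the choice to the investigator.

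**The concern.** Any display by non-randomised treatment is open to confounding. Here one part of the imbalance can be foreseen from the protocol itself. A patient who progressed in Part 1 and was then resected R0 or R1 contributes to DFS but can never appear in the cemiplimab group. If such patients recur more often than the rest, the cemiplimab curve will sit above the others with no help from the adjuvant drug.

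Protocol Section 3.2.3 says that Part 2 data could feed into the design of a later randomised adjuvant trial. A gap produced by the eligibility bar could then be read as a signal. The primary pCR analysis is not touched.

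**Working it through.** **1. Tracing a barred patient.** A patient progresses at the imaging before the third dose, goes to surgery and is resected R1.
- Protocol 9.1.5.1: no adjuvant cemiplimab; imaging for recurrence continues.
- Protocol 5.2.1 and SAP 4.4.2: in the DFS population.
- Protocol 9.1.6: post-surgical options are cemiplimab, radiation or observation.
- Protocol 11.3 and SAP 5.6.2: DFS shown by those three options.

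With cemiplimab closed, only radiation or observation is left. A toxicity stopper follows the same path.

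**2. The plan's own figure.** There is none for this display. The design figures (72 patients, raised to 76) concern pCR only. Every input below is an assumption.

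**3. Effect of the bar alone, with no effect of the adjuvant option.** Let f be the barred share of the DFS set, s the share on cemiplimab, b the event risk in eligible patients, and k the risk ratio in barred patients. The barred share among patients not on cemiplimab is q = f/(1 − s). Their risk is q·k·b + (1 − q)·b. The apparent hazard ratio is ln(1 − b) / ln(1 − risk off cemiplimab).

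All three cases use b = 0.20:

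| Case | f | s | k | q | Risk off cemiplimab | Apparent HR |
|---|---|---|---|---|---|---|
| Central | 0.10 | 0.5 | 2 | 0.20 | 0.20×0.40 + 0.80×0.20 = 0.240 | ln 0.80 / ln 0.76 = 0.81 |
| Weakest | 0.05 | 0.3 | 1.5 | 0.071 | 0.207 | 0.96 |
| Strongest | 0.15 | 0.7 | 3 | 0.50 | 0.400 | 0.44 |

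The grid was f from 0.05 to 0.15, s from 0.3 to 0.7 and k from 1.5 to 3. The ratio favours cemiplimab throughout because k was always set above 1. At k = 1 it is 1.00.

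**4. The same point as 2-year DFS.** Assume 70 resected patients: 30 cemiplimab, 20 radiation, 20 observation. Seven are barred (5 in radiation, 2 in observation). DFS is 80% in the others and 50% in the barred.
- Cemiplimab: 80%.
- Radiation: (15×0.80 + 5×0.50)/20 = 72.5%; 67.5% to 77.5% if barred DFS is 30% to 70%.
- Observation: (18×0.80 + 2×0.50)/20 = 77%; 75% to 79% over the same range.

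If only 2 of the 5 barred radiation patients had progressed, and the 3 toxicity stoppers carried ordinary risk, radiation is (18×0.80 + 2×0.50)/20 = 77%. The result depends heavily on how many of the barred are progressors.

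**5. Adding discretionary selection into radiation.** Assume 10% to 20% of eligible patients are high-risk (R1 or perineural), with the same risk ratio k, and 70% of them receive radiation. Other eligible patients split 50/15/35 over cemiplimab, radiation and observation; barred patients split evenly between radiation and observation. Over the same f and k, the apparent HR is 0.42 to 0.82 for cemiplimab versus radiation and 0.67 to 0.96 versus observation. This part follows from assumed clinical choice, not from the bar.

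**6. Precision.** With the group sizes of step 4, the approximate 95% margin on cemiplimab minus radiation is 1.96 × √(0.80×0.20/30 + 0.725×0.275/20) = ±24 points, well above the 7.5-point gap. For a true HR of 0.5 with 15 to 30 events split 1:1, power is 27% to 48%; 66 events are needed for 80%.

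**The case against.** The SAP, which governs the analysis, speaks of a summary for each group where the protocol speaks of a comparison. It plans no test or hazard ratio between options, and SAP 1.2.4 removed the subgroup efficacy analyses. Where no effect is estimated, calling the display unadjusted is a weak criticism. The protocol also says that its primary objective is neoadjuvant, not adjuvant, therapy, and no listed objective compares adjuvant options. All of this stands and limits the importance of the point. It does not remove it: three DFS summaries side by side will be read against each other.

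A second objection is that the placement of barred patients is inferred. Protocol Section 9.1 and its subsections list early discontinuers apart from those on radiation or observation. SAP 5.6.2 does not say whether a barred patient without radiation counts as observation, is shown separately or is left out. That is fair, and it is a reason to settle the matter in the SAP. If the three groups are meant to cover the whole DFS population, the placement follows.

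A third is that the illustrated gaps rest on assumed inputs and are small beside the sampling error. That also stands.

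**Conclusion.** The point holds as a cheap improvement to a secondary descriptive display. The bar is explicit, barred R0/R1 patients are in the DFS population, and a three-way split leaves them only radiation or observation. The direction favours cemiplimab on the assumption that progressors recur more often. The size cannot be known from the documents; the central HR of 0.81 and its range illustrate the mechanism and do not forecast a result.

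Two stronger readings are tempting, and the documents do not support them.

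- **That the protocol assigns positive-margin patients to radiation, so the groups differ in risk by rule throughout.** Nothing bars R1 patients from adjuvant cemiplimab. Section 3.2.3 cites guidelines and then stresses individual decisions, and the choice is the investigator's. Selection of positive-margin or perineural patients into radiation is likely, but it is ordinary confounding by indication.
- **That the cemiplimab group loses all its worst patients.** No section shows that toxicity stoppers recur more often. The argument about risk rests on the progressors.

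**What to change.** In SAP Section 5.6.2:

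1. Limit the DFS summary by adjuvant option to R0/R1 patients without Part 1 progression and without permanent discontinuation of neoadjuvant drug for toxicity. Define progression from both Part 1 imaging assessments, so that progression first seen before surgery is covered as well.
2. Show the barred R0/R1 patients as a separate group, so that no data are lost. The overall DFS analysis stays as planned.
3. Tabulate stage, R0/R1 status and pathologic response by option. Do not split the DFS curves by these factors, because the cells would be too sparse.
4. State that the groups are not randomised and not comparable.

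Step 1 returns the bar-driven ratio to 1.00 by construction under the model above. It does not remove discretionary selection into radiation; steps 3 and 4 make that visible. Multivariable adjustment is not a workable substitute: an assumed 15 to 25 events over about 6 parameters gives roughly 2.5 to 4 events per parameter.

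The cost is SAP wording and programming. Resection status, pathology, Part 1 imaging, reasons for discontinuation and stage are already needed elsewhere in the study. The downside is somewhat smaller groups and wider intervals.
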